7.1 Diseases and Therapeutic Area

Chronic non-cancer pain describes back, musculoskeletal, abdominal, headache and other neurologic pain without an evidence of cancer¹.

¹ Dowell et al., 2016

Today, chronic pain is one of major health care problems in Europe. For instance, a large telephone survey in 15 European countries and Israel showed that chronic non-cancer pain of moderate to severe intensity has a prevalence of 19 % affecting the quality of patient's social and working lives². Common treatment of moderate to severe chronic pain includes opioids, analgesic anticonvulsants³ and low-dose cyclic antidepressants⁴. Analgesic anticonvulsants and low-dose cyclic antidepressants can have serious adverse effects⁵. But also the tendency of increased prescriptions of opioid analgesics leads to a discussion about potential harms of this medication⁶.

7.2 Rationale

Among patients receiving opioids for treatment of noncancer pain, recent research in North America showed a strong association between doses and opioid-related mortality, especially at dosages exceeding thresholds recommended in recent guidelines⁷. However, the focus on over-dosage may underestimate overall opioid-related mortality and data on death associated with opioid use in a population-based cohort of chronic non-cancer pain patients in Europe is scarce. Especially comparative studies studying the safety of long-term opioid therapy relative to non-opioid medication for chronic noncancer pain are needed in a European context.

² Breivik et al., 2006

³ Moore et al., 2011

⁴ Carragee et al., 2005

⁵ Ray et al., 2004

⁶ Okie et al., 2010

⁷ Ray et al., 2016

8. Research Question and Objectives

8.1 Primary objectives

Objective of this study is to investigate the association between mortality among patients with chronic noncancer pain with long-term opioid-therapy compared to non-opioid pain medication (nonsteroidal anti-inflammatory drugs (NSAIDs, Metamizole), anticonvulsants, antidepressants).

In order to address the primary objective, following hypotheses will be examined in the study:

- How many patients with chronic noncancer pain on long-term opioid therapy and patients with non-opioid pain medication died in time period of five years?
- Which demographic factors, comorbidities and comedication predict mortality and time to mortality among patients with chronic noncancer pain on long-term opioid therapy and of patients with non-opioid pain medication?
- Does mortality differ between patients with chronic noncancer pain on long-term opioid therapy compared to patients with non-opioid pain medication in time period of five years?

8.2 Secondary objectives

In addition, present study aims to determine the risk of addiction/ abuse and hospital admissions among opioid users with chronic non-cancer pain compared to patients with non-opioid pain medication.

The secondary objectives will be addressed with following hypotheses:

- How often do patients on long-term opioid therapy and patients with non-opioid pain medication being hospitalized and how long do they stay in hospital?
- Does the number of hospitalizations and length of stay in hospital differ between patients on long-term opioid therapy compared to patients with non-opioid pain medication in time period of five years?
- How many misuse and addiction diagnoses were coded in outpatient sector for patients on long-term opioid therapy and patients with non-opioid pain medication in time period of five years?
- Does the number of outpatient misuse and addiction diagnoses differ between patients on long-term opioid therapy compared to patients with non-opioid pain medication in time period of five years?
- How many sick leave days do patients on long-term opioid therapy and patients with non-opioid pain medication have in time period of five years?

9. Research Methods

9.1 Study Design

This is a retrospective observational cohort study based on an anonymized German health claims database. This database contains data on around 4 million insured people from 69 German statutory health insurances (SHI). This research database is a complete, longitudinal claims dataset of approx. 7 million individual patients (ca. 10% of the statutory insured population of Germany) between 2012 and 2017. The analyses for this study will be done on a 4 million patients subset that is stratified by age

and gender based on the 2013 population structure of Germany as reported by the German Federal Statistical Office DeStatis.

This study consists of two cohorts: opioid and non-opioid patients. Only patients who started their therapy between 2013 and 2017 and had no therapy in 2012 (therapy naïve patients) will be included in the study.

Exposure time is defined as max. 5 years after the initial prescription for each patient, so that exposure time is max. 60 months per patient.

Exposure time may end before the end of study if patient died, stopped treatment (end of follow-up after 1 year without treatment with opioids / other pain medication), changed treatment group (from opioids to other pain medication or vice versa) or was lost to follow up due to other reasons (e.g. change of insurance), whichever occurs first.

9.2 Setting and Study Population

The database contains data on around 4 million insured people from 69 German statutory health insurances (SHI). German SHI system comprises of approximately 120 independent health insurance companies. Funds paid by these SHI to any provider of health care (e.g. hospitals, physicians, pharmacies, psychotherapists and physiotherapists) represent almost the complete picture of the total health care costs of individual patients. All health insurance data can be linked to patients' demographics including age and gender. Health care data in the database include:

- Patient demographics:
 - age
 - gender
 - date of death

- region of residence
- insurance status
- date of insurance start and end
- Hospital care:
 - main diagnosis (ICD-10-GM codes) and additional diagnoses
 - procedures and surgeries
 - date of hospital admission
 - reason for admission (e.g. accident, emergency, normal)
 - date of end of hospital stay
 - reason of end of hospital stay (e.g. regular discharge from hospital, death)
 - DRG-Code
 - costs
- Outpatient care:
 - diagnoses (ICD-10-GM codes)
 - quarter in which the diagnosis was documented
 - procedures performed (EBM codes, e.g. laboratory tests, radiology, echocardiography) and date of procedure
 - type of specialist that documented the diagnosis and performed the procedure (e.g. cardiologist, general practitioner)
 - costs
- Pharmaceutical claims:

- drug dispensed (PZN code, which identifies medications at the package level) – this is mapped to ATC codes and DDDs
- quantity dispensed
- day of prescription
- day of dispensing
- type of specialist prescribing the medication (e.g. general practitioner)
- costs of drugs dispensed from the perspective of the statutory health insurance (without individual rebates between insurance and pharmaceutical companies)
- Physical therapy and technical aids:
 - type of therapy (e.g. massage, occupational therapy, walker, wheel chair)
 - quantity prescribed
 - type of care provider
 - start and end date
 - costs
- Sick leave:
 - diagnoses that cause sick leave
 - duration of sick leave
 - start date of sick leave
 - end date of sick leave

- type of specialist that filled out the sick leave form (e.g. general practitioner)
- costs of sick leave

To note, data are adjusted within the database to Germany's typical age and sex distribution in accordance with the Federal Statistical Office based on the year 2013 (<https://www-genesis.destatis.de/genesis/online>) to foster its overall representativeness in regards to the population in Germany. Privately insured patients in Germany are not included in this database.

All data used are explicitly approved by the involved statutory health insurances for health care research usage according to § 287 or § 75 of the German social security law (SGB V).

Source population of the study are patients covered by the German Health Claims database over 2012-2017 years.

Study population are patients from the source population meeting inclusion (eligibility) criteria (see section 9.2.2).

9.2.1 Study Period

Due to data protection regulations in Germany, only an extract of maximum 6 years of data coverage could be available for the research purposes: 1st January 2012 to 31st December 2017.

The **baseline period** is defined as the period prior to the date of first diagnosis of diagnoses or first opioid or non-opioid treatment initiation as described in inclusion criteria (Chapter 9.2.2.1). The baseline assessment period endures between January 01, 2012 and first study medication prescription.

Index treatment is defined as the date of first opioid or non-opioid treatment prescription between 1st January 2013 and 31st December 2017.

Exposure time is defined as time between index treatment and December 31, 2017. Considering data availability of a maximum of 6 years and prescription in a required time period of 60 months, exposure time endures maximum five years. Thus, patients can be censored at death (death date in the linked records), last known record for the patient in the German health claims database, switching of treatment groups (from opioid group to non-opioid group or vice versa), 12 months without opioid/non-opioid treatment or 31st December 2017 (end of latest data cut), whichever comes first.

[figure not shown]
The **outcomes** will be assessed between index treatment and 31.12.2017.

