9.2.2 Patient Eligibility

9.2.2.1 Inclusion Criteria

For the purposes of this study, the requested extraction of the database consists of population of patients with chronic non-cancer pain corresponding to the following criteria. Inclusion and exclusion criteria are also provided in Figure 2.

Figure 2: Inclusion and exclusion criteria

Cohort A

- Patients are included in the long-term opioid group if they started an opioid-therapy between 2013 and 2017 and received consecutive prescriptions for opioid medications over a minimum of 3 quarters, over a 60-month period between January 1, 2013, and December 31, 2017. The treatment will be assessed using the ATC codes of opioid treatment N02AA01, N02AA05, N02AB03, N02AE01, N02AX02, N02AX01, N02AX06 (see also Table 9-1) reported in reimbursed medicines to patients.

- Patients are only included if they have been diagnosed in at least three quarters in the study period with one of the following diagnoses: R51, R52*, M00*-M99*, G43*-G44*, G50.0 or G50.1, F45.4*, G62*, or E10.4*-E14.4 plus G63.3. At least one diagnoses must be between 1 January 2012 and index treatment and main and secondary hospital diagnoses (*i.e. Haupt- und Nebendiagnosen*) will be used to include the patients.

Cohort B

- Patients with non-opioid pain medication are included, if they received a medication therapy with anticonvulsants (gabapentin, pregabalin, carbamazepine), antidepressants or non-opioid analgesics (NSAIDs, Metamizole) over a minimum of 3 quarters, over a 60-month period between January 1, 2013, and December 31, 2017. The non-opioid treatment will be assessed using the ATC codes (N03AX12, N03AX16, N03AF01, see also Table 9-1) of treatment reported in reimbursed medicines to patients.
- Patients are only included if they have been diagnosed in at least three quarters in 2012 with one of the following diagnoses: R51, R52*, M00*-M99*, G43*-G44*, G50.0 or G50.1, F45.4*, G62*, or E10.4*-E14.4 plus G63.3. At least one diagnoses must be between 1 January 2012 and index treatment and main and secondary hospital diagnoses (*i.e. Haupt- und Nebendiagnosen*) will be used to include the patients.

All diagnoses that lead to patient inclusion when coded between 01.01.2012 and index treatment and in at least three quarters within the study period are provided in Table 9-2 below.

Table 9-1: List of ATC codes of study opioid and non-opioids

Name	ATC Code
Study opioids	
Morphine	N02AA01
Oxycodone	N02AA05
Fentanyl	N02AB03

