9.4.1 Exposure Assessment

Opioid and non-opioid treatments will be assessed using ATC and PZN codes (see Table 9-1) as described below:

- **Opioid Treatment** received between January 1st 2012 and December 31st 2016 in at least 3 quarters, over a 60-month period based on ATC code N02A%.
- **Non-Opioid Treatment** (NSAIDs, anticonvulsants, antidepressants) received between January 1st 2012 and December 31st 2016 in at least 3 quarters, over a 60-month period, based on ATC code in Table 9-1.
- **Treatment Dosage** will be assessed based on DDD assessment per ATC code using DIMDI data. Dosage will thus be calculated as medication dose per day based on the average prescription per year of the year. The number of medication claims, the number of drug packages and DDD per package are used to estimate the daily dose.

- Treatment dosage of opioid treatment will be defined based on morphine equivalence. The low dosage is thus defined as less than 60mg/d morphine equivalence. The intermediate dosage will be defined as a dosage between 60mg/d and 120mg/d morphine equivalence. The high dosage will be defined as 120mg/d morphine equivalence or higher.
- Treatment dosage for non-opioid treatment is defined as follows:
 - Anticonvulsive: based on gabapentin equivalence. The low dosage is thus defined as a daily dosage of less than 600mg/d gabapentin equivalents and a high dosage of 600mg/d or more gabapentin equivalents.
 - Antidepressants: via standard psychiatric dose according to AKDÄ (2006) recommendations: daily doses below the minimum standard psychiatric dose will be defined as "low", dosages above as "high". The standard psychiatric dose per ATC can be seen in Table 9-5.

Table 9-5:: Standard psychiatric doses as threshold for low/high dosage

Active substance	ATC code	Minimum standard psychiatric dose
Amitriptylin	N06AA09	100
Amitriptylinoxid	N06AA09	100
Clomipramin	N06AA04	100
Desipramin	N06AA01	100
Dibenzepin	N06AA08	240
Doxepin	N06AA12	100
Imipramin	N06AA02	100
Maprotilin	N06AA21	100
Nortriptylin	N06AA10	50

Trimipramin	N06AA06	100
Citalopram	N06AB04	20
Escitalopram	N06AB10	10
Fluoxetin	N06AB03	20
Fluvoxamin	N06AB08	100
Paroxetin	N06AB05	20
Sertralin	N06AB06	50
Moclobemid	N06AG02	300
Tranylcypromin	N06AF04	20
Venlafaxin	N06AX16	75
Duloxetin	N06AX21	60
Reboxetin	N06AX18	8
Mianserin	N06AX03	60
Mirtazapin	N06AX11	15
Trazodon	N06AX05	200

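### The three-quarter exposure rule is not tied to index or to follow-up, so a patient can qualify on prescriptions filled after their own exit

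*Protocol*

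**What the plan says.** - **Start of the clock (9.2.1):** "Index treatment is defined as the date of first opioid or non-opioid treatment prescription between 1st January 2013 and 31st December 2017".
- **Cohort A entry (9.2.2.1):** the patient started opioid therapy in 2013–2017 and "received consecutive prescriptions for opioid medications over a minimum of 3 quarters, over a 60-month period between January 1, 2013, and December 31, 2017".
- **Cohort B entry (9.2.2.1):** treatment "over a minimum of 3 quarters, over a 60-month period between January 1, 2013, and December 31, 2017. The non-opioid treatment" (the closing words open the next sentence). The quarters are not required to be consecutive.
- **Exposure definition (9.4.1):** opioid treatment is "received between January 1st 2012 and December 31st 2016 in at least 3 quarters, over a 60-month period based on ATC code N02A". The non-opioid line is parallel. Neither asks for consecutive quarters, and the calendar window differs from the one in 9.2.2.1.
- **Exit (9.2.1):** death, last record, change of treatment group, "12 months without opioid/non-opioid treatment or 31st December 2017 (end of latest data cut), whichever comes first". Section 9.1 and the follow-up paragraph of the opening summary also end follow-up at a 12-month gap or a change of group.
- **Mortality rate (9.4.2.1):** the censoring list has only death, last record and the end of 2017. Gap and change of group are absent.

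**The concern.** Three rules meet here: when the clock starts, what makes a patient a long-term user, and when the clock stops. The first and third follow the patient's own course. The second is attached only to a calendar window. Nothing in the text says that the qualifying quarters begin at index or fall before exit.

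A patient can therefore be placed in a long-term cohort because of prescriptions filled after leaving follow-up. To fill them the patient had to be alive, so all of that patient's analysed time is death-free by construction. A death after exit, including one during the therapy that earned the label, is not counted under the gap and switch rule. The primary objective in section 8.1 concerns mortality on long-term therapy, and for these patients the analysed time does not represent it.

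The two cohorts are also worded differently: scattered quarters satisfy the rule in Cohort B but not the Cohort A rule in 9.2.2.1. If the share of such patients differs between cohorts, the comparison is affected. Propensity matching on characteristics before index cannot correct for selection on events after exit.

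**Working it through.** The protocol gives no figure to reproduce on this point. The check applies its dates to constructed prescription histories.

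**Rules applied**
- Index = first study prescription from 1 January 2013 (9.2.1).
- Exit = last prescription before a gap + 12 months (9.1, 9.2.1).
- Qualification = three consecutive calendar quarters for Cohort A, any three quarters for Cohort B (9.2.2.1).

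| History | Index | Exit | Rule completed | Order |
|---|---|---|---|---|
| Cohort A, unbroken: 15 Feb, 15 May, 15 Aug 2013 | 15 Feb 2013 | 15 Aug 2014 | 15 Aug 2013 | qualifies before exit |
| Cohort B, scattered: 15 Feb 2013, 15 Aug 2014, 15 Feb 2016 | 15 Feb 2013 | 15 Feb 2014 | 15 Feb 2016 | exit precedes qualification by 24 months |
| Cohort A, gap: 15 Feb 2013, then 15 Feb, 15 May, 15 Aug 2016 | 15 Feb 2013 | 15 Feb 2014 | 15 Aug 2016 | run starts 730 days after exit |

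**Reading the table**

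1. The scattered Cohort B patient leaves follow-up after one prescription, six months before the second. All 12 analysed months are death-free.
2. The Cohort A patient with a gap contributes the same 12 months, all before the 2016 run. The duration covariate (last minus first prescription, 9.3.2 and 9.4.1) is 42 months, from February 2013 to August 2016, against 12 months of follow-up.
3. The therapy-naive exclusions do not remove these patients. Section 9.2.2.2 looks only at 2012, the opening summary looks at the time before index, and the isolated first prescription is itself the index.
4. Under the shorter list in 9.4.2.1 both patients stay in follow-up through the later prescriptions. The time from index to the third quarter is still death-free: 36 months in the Cohort B history (February 2013 to February 2016) and 42 months in the Cohort A history. Even the unbroken patient has about 6 such months (15 February to 15 August 2013).

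**When the Cohort A gap pattern can occur.** The last possible run is Q2–Q4 2017, so its first prescription falls on or before 30 June 2017. With a gap of more than 12 months, index can be as late as 29 June 2016. From 1 January 2013 that is 1,276 of 1,826 days, or 1,276/1,826 = 70% of possible index dates. This is a share of dates, not of patients.

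**The case against.** **Cohort A can be read more kindly.** Its sentence joins starting an opioid therapy to receiving consecutive prescriptions, and the natural sense may be one run from the start. On that reading the Cohort A gap history does not qualify. This stands as a possible reading, but no text fixes it, and it does not help Cohort B or section 9.4.1.

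**The mortality rate uses another censoring list.** A reader might infer that deaths on the later therapy are lost throughout and that both reported rates are too low. The protocol does not support that: under 9.4.2.1 follow-up continues past the gap and such deaths count. The loss applies to the time-to-event follow-up governed by 9.1 and 9.2.1. What remains under 9.4.2.1 is the death-free time before the third quarter.

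**A reader might put a size on it.** Suppose a share f of a cohort adds 1.0 death-free year each and the others average 2.0 years. The crude rate is then multiplied by 2(1−f)/[2(1−f)+f]: 1.9/1.95 = 0.974 at f = 5%, 1.6/1.8 = 0.889 at 20%, and 1.4/1.7 = 0.824 at 30%. With 5% in Cohort A and 20–30% in Cohort B, the rate ratio rises by a factor of 1.10–1.18. Swapping the shares gives 0.91–0.85, and equal shares give no change. Every input is assumed, the quantity is a crude rate ratio rather than the Cox hazard ratio, and the rate in 9.4.2.1 is not censored this way. These figures do not estimate the bias.

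**Follow-up is not always 12 months.** Two prescriptions 8 months apart followed by a gap give 8 + 12 = 20 months.

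**Figures are not visible.** The study-period figure in 9.2.1 and Figure 2 in 9.2.2.1 might show an anchor. If so, the text should state it.

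**Conclusion.** The point holds as a defect in how eligibility, index and exit fit together. It is clear in Cohort B and in the wording of 9.4.1. In Cohort A it depends on whether the consecutive run must start at index. Under the exit rule of 9.1 and 9.2.1, affected patients are labelled long-term users, contribute only death-free time, and have later deaths left out. Because the cohorts are worded differently, their shares may differ and the hazard ratio can be biased. The protocol reports nothing on prescribing gaps, so neither the size nor the direction of that bias can be computed. The conclusion rests on the written text and on the general exit rule applying to the Cox analysis. Under 9.4.2.1 the problem narrows to death-free time between index and the third quarter.

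**What to change.** 1. In 9.2.2.1 and 9.4.1, count toward the three-quarter rule only prescriptions from index onward and before the patient's first 12-month gap or change of group. Use the same wording and the same calendar window in both cohorts, and say whether the quarters must be consecutive.
2. Start time at risk when the third qualifying quarter is reached. Step 1 alone stops patients qualifying after exit but leaves everyone unable to die between index and the third quarter.
3. Reconcile the censoring lists in 9.2.1 and 9.4.2.1, so that the mortality rate and the Cox model use the same follow-up or the difference is stated and justified.

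Moving index to a later qualifying run is not a simple alternative. The earlier prescription would then precede index, which the opening summary excludes, and the design in 9.1 and 9.2.2.2 is built on therapy-naive patients at their initial prescription. Those rules would have to change with it.

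**Cost:** a short change to the cohort definition and follow-up start, plus a change to the cohort-building program. Patients with isolated or scattered prescriptions leave the analysis, as do deaths before the third quarter. The result then describes mortality among patients who have completed three quarters of treatment, and the report should say so.

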9.2.2 Patient Eligibility

9.2.2.1 Inclusion Criteria

For the purposes of this study, the requested extraction of the database consists of population of patients with chronic non-cancer pain corresponding to the following criteria. Inclusion and exclusion criteria are also provided in Figure 2.

Figure 2: Inclusion and exclusion criteria

Cohort A

- Patients are included in the long-term opioid group if they started an opioid-therapy between 2013 and 2017 and received consecutive prescriptions for opioid medications over a minimum of 3 quarters, over a 60-month period between January 1, 2013, and December 31, 2017. The treatment will be assessed using the ATC codes of opioid treatment N02AA01, N02AA05, N02AB03, N02AE01, N02AX02, N02AX01, N02AX06 (see also Table 9-1) reported in reimbursed medicines to patients.

- Patients are only included if they have been diagnosed in at least three quarters in the study period with one of the following diagnoses: R51, R52*, M00*-M99*, G43*-G44*, G50.0 or G50.1, F45.4*, G62*, or E10.4*-E14.4 plus G63.3. At least one diagnoses must be between 1 January 2012 and index treatment and main and secondary hospital diagnoses (*i.e. Haupt- und Nebendiagnosen*) will be used to include the patients.

Cohort B

- Patients with non-opioid pain medication are included, if they received a medication therapy with anticonvulsants (gabapentin, pregabalin, carbamazepine), antidepressants or non-opioid analgesics (NSAIDs, Metamizole) over a minimum of 3 quarters, over a 60-month period between January 1, 2013, and December 31, 2017. The non-opioid treatment will be assessed using the ATC codes (N03AX12, N03AX16, N03AF01, see also Table 9-1) of treatment reported in reimbursed medicines to patients.
- Patients are only included if they have been diagnosed in at least three quarters in 2012 with one of the following diagnoses: R51, R52*, M00*-M99*, G43*-G44*, G50.0 or G50.1, F45.4*, G62*, or E10.4*-E14.4 plus G63.3. At least one diagnoses must be between 1 January 2012 and index treatment and main and secondary hospital diagnoses (*i.e. Haupt- und Nebendiagnosen*) will be used to include the patients.

All diagnoses that lead to patient inclusion when coded between 01.01.2012 and index treatment and in at least three quarters within the study period are provided in Table 9-2 below.

Table 9-1: List of ATC codes of study opioid and non-opioids

Name	ATC Code
Study opioids	
Morphine	N02AA01
Oxycodone	N02AA05
Fentanyl	N02AB03
Buprenorphine	N02AE01
Tramadol	N02AX02
Tilidine	N02AX01
Tapentadol	N02AX06
Study non-opioids (anticonvulsive)	
Gabapentin	N03AX12
Pregabalin	N03AX16
Carbamazepine	N03AF01
Study non-opioids (antidepressants)	
Non-selective monoamine reuptake inhibitors	N06AA*
Selective serotonin reuptake inhibitors	N06AB*
Monoamine oxidase inhibitors, non-selective	N06AF*
Monoamine oxidase A inhibitors	N06AG*
Other antidepressants	N06AX*
Study non-opioids (Nonsteroidal anti-inflammatory drugs)	
Butylpyrazolidines	M01AA*
Acetic acid derivatives and related substances	M01AB*
Oxicams	M01AC*
Propionic acid derivatives	M01AE*
Fenamates	M01AG*
Coxibs	M01AH*

Other antiinflammatory and antirheumatic agents, non-steroids	M01AX*
Study non-opioids (others)	
Metamizole	N02BB02

Table 9-2: List of included ICD-10 diagnoses for both cohorts

Name	ICD-10 Code
Diseases of the musculoskeletal system and connective tissue	M00* - M99*
Headache	R51
Pain, not elsewhere classified	R52*
Migraine	G43*
Other headache syndromes	G44*
Trigeminal neuralgia	G50.0
Atypical facial pain	G50.1
Persistent somatoform pain disorder	F45.4*
Other and unspecified polyneuropathies	G62*
Diabetes mellitus with neurological complications	E10.4-E14.4
AND	
Polyneuropathy in diseases classified elsewhere	G63.3

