9.4.2.1 Primary endpoint

Primary endpoint is **death** by any course in the study follow-up. Death will be assessed during the follow-up period by number of patients who deceased during follow-up period (2013 – 2017) via the date of death in German claims data base. Additionally, mortality rate will be estimated as number of patients who died during the follow-up divided by person-time

of follow-up, censoring at time of death, last known record for the patient in the database, or 31st December 2017 (end of latest data cut), whichever is earlier.

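### Risk time starts at the first prescription, but cohort entry needs prescriptions in three quarters: mortality rates are too low in both cohorts, and the hazard ratio is biased if qualifying times differ

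*Protocol*

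**What the plan says.** **Start of follow-up.** Section 9.2.1: "Index treatment is defined as the date of first opioid or non-opioid treatment prescription between 1st January 2013 and 31st December 2017". The same section adds: "Exposure time is defined as time between index treatment and December 31, 2017". It also has outcomes assessed from the index treatment onwards. Section 9.1 likewise runs exposure time from the initial prescription, for at most five years.

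**Entry to the cohorts.** Section 9.2.2.1 requires that opioid patients "received consecutive prescriptions for opioid medications over a minimum of 3 quarters, over a 60-month period between January 1, 2013, and December 31, 2017". Non-opioid patients need antidepressants, anticonvulsants or "non-opioid analgesics (NSAIDs, Metamizole) over a minimum of 3 quarters, over a 60-month period between January 1, 2013, and December 31, 2017". Sections 9.1 and 9.2.2.2 restrict both cohorts to therapy-naive patients.

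**Primary endpoint.** Section 9.4.2.1: "mortality rate will be estimated as number of patients who died during the follow-up divided by person-time" of follow-up. It lists the censoring events and names no start date, so the start is the index of section 9.2.1.

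**Diagnosis quarters.** Section 9.2.2.1 says for cohort A: "Patients are only included if they have been diagnosed in at least three quarters in the study period with one of the following diagnoses". For cohort B it says: "Patients are only included if they have been diagnosed in at least three quarters in 2012 with one of the following diagnoses". Its closing sentence, on both cohorts, refers to diagnoses "coded between 01.01.2012 and index treatment and in at least three quarters within the study period are provided in Table 9-2 below". The synopsis places the three diagnosis quarters before the first opioid claim.

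**Treatment quarters.** Section 9.4.1 gives both treatments the same three-quarter minimum and does not ask for consecutive prescriptions in either. Its paragraph on treatment duration derives a minimum of 9 months from the three-quarter criterion.

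**The concern.** The entry condition lies in the future of the index date. A patient who dies before a prescription in the third quarter belongs to neither cohort. A patient who survives to that prescription is included, and the time spent getting there is counted as time at risk. This is immortal time.

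Two results are at stake. The first is the mortality rate in each cohort, which is part of the primary endpoint: its denominator includes time that could not contribute a death. The second is the Cox comparison. Equal deathless spans cancel out of the hazard ratio; unequal spans do not, and the cohort that qualifies sooner then appears to have the higher mortality.

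Nothing in the protocol offsets this. Only dosage is time-varying (section 9.3.2). The one sensitivity analysis concerns cancer diagnoses (section 9.8.2). Section 9.10.1.3 calls selection bias less likely. Matching on baseline variables cannot remove person-time created by a condition met after baseline.

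**Working it through.** The protocol gives no event count, mean follow-up or expected hazard ratio, so there is no figure of its own to reproduce.

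**1. Length of the deathless span.** Read the rule as three adjacent calendar quarters, counting the index quarter. The shortest span runs from the last day of the first quarter to the first day of the third: 31 December 2013 to 1 April 2014 = 91 days. The longest runs from the first day of the first to the last day of the third: 1 April to 31 December 2017 = 274 days. That is about 3.0 to 9.0 months. If three quarters means elapsed time, as the 9-month minimum in section 9.4.1 implies, the span is at least about 9 months. If the quarters need not be adjacent, it can be longer.

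**2. Effect on the mortality rate.** Let r be the true rate after qualification, L the mean lag and F the mean follow-up from first prescription. All deaths occur in the time F − L, but the denominator is F:

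reported rate = r × (1 − L/F)

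Take r = 100 and 200 per 10,000 person-years, the expectation in section 9.3.1. F is not given and is assumed.

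| Lag L | F = 2 years | F = 3 years | F = 5 years |
|---|---|---|---|
| 3 months | 87.5 and 175 | 92 and 183 | 95 and 190 |
| 6 months | 75 and 150 | 83 and 167 | 90 and 180 |
| 9 months | 62.5 and 125 | 75 and 150 | 85 and 170 |

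As one guide to F, assume index dates uniform over 2013–2017, a 6-month lag and no other censoring. Follow-up among those who qualify then ranges from 0.5 to 5 years, with mean (0.5 + 5)/2 = 2.75 years. The deathless share is 0.5/2.75 = 18%.

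**3. Effect on the hazard ratio.** Assumptions: a fixed lag in each cohort, a constant hazard of 150 per 10,000 person-years after it, index dates uniform over five years, equal cohort sizes, and entry only if qualified by the end of data. With λ = 0.015 per year, the proportion at risk in cohort k at time t is

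- Y_k(t) = (5 − L_k)/5 for t < L_k
- Y_k(t) = [(5 − t)/5] × exp[−λ(t − L_k)] for t ≥ L_k

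Deaths occur only for t ≥ L_k, at rate λY_k(t). The log hazard ratio b (A versus B) solves the large-sample Cox score equation: the sum over deaths of [1 if in A, otherwise 0] − e^b Y_A/(e^b Y_A + Y_B) equals zero.

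| Lag A / lag B | True HR | HR from first prescription | With 0.3 per year extra censoring after qualification |
|---|---|---|---|
| 6 / 6 months | 1.00 | 1.00 | 1.00 |
| 6 / 9 months | 1.00 | 1.12 | 1.18 |
| 9 / 6 months | 1.00 | 0.89 | 0.85 |

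With hazards of 100 or 200 per 10,000 person-years instead, the last two rows without extra censoring stay at 1.12 and 0.89. A true ratio of 2.00 with equal 6-month lags gives 2.00.

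A simulation with variable lags agrees. With 0.25–0.75 years in both cohorts the ratio is unbiased. With cohort B stretched to 0.25–1.5 years, a true 1.00 becomes 1.17–1.23; with cohort A stretched instead, 0.82–0.86. In these runs, entering patients at the qualifying date recovers the true rates and ratios within simulation error.

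**4. Are the lags equal?** The entry rules do not say. Only cohort A is told that prescriptions must be consecutive, which would tend to lengthen the lag in B. Only cohort A may complete its diagnosis quarters after the index, which would tend to lengthen the lag in A. Section 9.4.1, the closing sentence of 9.2.2.1 and the synopsis each give a different version.

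**The case against.** The strongest reply is that the primary objective is comparative, and with equal lags the hazard ratio is about right. That stands: what is certain is the understatement of the rates, while bias in the Cox contrast is conditional.

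The lags used for the hazard ratio are indeed assumptions. By the same calculation a 1-month difference (6 against 7 months) gives 1.04 and a 2-month difference 1.08. The planned model also adjusts for the propensity score, comorbidity, index quarter, dosage and total treatment duration, the last itself known only after the index date. So 1.12 and 0.89 illustrate the mechanism and do not estimate the bias in the planned analysis.

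Cohort B is not said to allow gaps; the word consecutive is merely absent. The 12-month treatment-gap censoring also limits how long an uncensored lag can become. Both points are fair, and neither removes the deathless time. The 5-year column is only a limit, since it requires everyone to start at the beginning of 2013 with no earlier censoring.

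Finally, identical rules would not guarantee equal lags, because prescribing patterns can differ. That is a reason to move the start of risk time as well as to harmonise the wording. Nor can the matter be left to an analysis plan: the protocol itself fixes the index, the start of exposure, the outcome window and the entry rule.

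**Conclusion.** Wrong as written, and it must be corrected before analysis. Under every reading of the three-quarter rule the mortality rates of the primary endpoint are too low in both cohorts. Over the assumed mean follow-up of 2 to 5 years and lags of 3 to 9 months, the shortfall is 5% to 37.5%. It is 18% for a 6-month lag with uniform index dates and no other censoring.

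The hazard ratio is sound only if both cohorts take equally long to qualify. A 3-month difference would move a true 1.00 to about 1.12 or 0.89 under the stated assumptions. The document fixes neither the direction nor the size of that bias, because its entry rules conflict. The separate point on the 9-month minimum duration is minor: it holds only if three quarters means elapsed time.

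**What to change.** - In both cohorts, start risk time on the date the treatment criterion is met, that is, the first prescription in the third qualifying quarter, by delayed entry or a landmark. Say so in sections 9.1, 9.2.1 and 9.4.2.1. With delayed entry, age, baseline covariates and matching can stay anchored at the first prescription.
- State one treatment rule (consecutive or not) and one diagnosis window for both cohorts, each satisfied by that date. Reconcile the synopsis and sections 9.2.2.1 and 9.4.1 with it.
- In the duration paragraph of section 9.4.1, either replace the 9-month minimum with the calendar-quarter value of about 3 months, or state that three quarters means elapsed time.

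The cost is wording, a re-programmed start date and less person-time (18% less in the 6-month, 2.75-year case). Prescription and dispensing dates are already in the database (section 9.2). Moving the start date removes no deaths, because the time removed contains none. Harmonising the entry rules may change who is included and so remove some patients and events; that number can be counted in the data before the rule is fixed.
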